#### 14.2.2. ORR (for confirmed+unconfirmed responses) based on investigator-assessed tumor evaluation

Objective Response Rate, considered for confirmed + unconfirmed responses as per local radiologist/investigator assessment, will be analyzed in the same manner as the primary analysis for the ES and FAS.

The best overall response (BOR) for confirmed + unconfirmed responses will be derived as per RECIST guideline version 1.1.

Only tumor assessments performed before the start of any further antineoplastic therapies (i.e. any additional secondary antineoplastic medication or anti-cancer surgery or radiotherapy) and not later than 30 days after last study treatment administration will be considered in the assessment of BOR. Clinical deterioration or clinical progression noted on the end-of-treatment eCRF will not be considered as documented disease progression.

The BOR for each subject is determined from the sequence of overall (lesion) responses according to the rules displayed in section 14.1.

- CR: at least one determination of CR before progression
- PR: at least one determination of PR before progression
- SD: at least one SD assessment (or better)  $\geq 6$  weeks after start of treatment (and not qualifying for CR or PR).
- PD: early progression  $\leq 9$  weeks after first study treatment administration (and not qualifying for CR, PR or SD).
- NE = all other cases (i.e. not qualifying for confirmed CR or PR and without SD  $\geq 6$  weeks or early progression  $\leq 9$  weeks after first study treatment administration)

Best overall response (confirmed+unconfirmed) will be summarized, with reasons for having unknown status in Non-Evaluable patients, including:

- No baseline assessment, no measurable disease at baseline

- No adequate post-baseline assessment
- All post-baseline assessments have overall response of “NE”
- New antineoplastic therapy (i.e. any additional secondary antineoplastic medication or anti-cancer surgery or radiotherapy) started before first post-baseline assessment
- SD occurred <6 weeks after first study treatment administration
- Progression >9 weeks after first study treatment administration

The following table, based on Table 3 from the RECIST 1.1 guidelines, summarizes the algorithm describing how Best Overall Response (BOR) for confirmed and unconfirmed response is determined from the overall tumor assessments. The order used to determine the BOR is CR>PR>SD>PD, ignoring visits with missing tumor assessments.

All assessments following an assessment of PD will be excluded from the derivation of BOR.

**Table 11: Best Overall Response (confirmed+unconfirmed)**

Case	Timepoint (Best response with CR>PR>SD>PD>NE)	Best Overall Response (confirmed+unconfirmed)
1	CR	CR
2	PR	PR
3	SD	SD or PD or NE 
 
• SD, if SD assessment <math>\geq 6</math> weeks, i.e. 42 days after date of first administration of study treatment,
 
• otherwise PD if subsequent PD assessment <math>\leq 9</math> weeks, i.e. 63 days after date of first administration of study treatment,
 
• otherwise NE
 

4	PD	PD or NE 
 
• PD if PD assessment <math>\leq 9</math> weeks, i.e. 63 days after date of first administration of study treatment,
 
• otherwise NE
 
 Ignore all assessments after initial overall response of PD.
5	NE	NE Where all assessments are Not evaluable.

\* As per Table 3 from RECIST guideline (version 1.1).

### **Objective Response Rate**

The **Objective Response Rate** will be defined as the sum of CR and PR (confirmed+unconfirmed) rate:

$$ORR = \frac{\sum(\#CR + \#PR)}{N}$$

with:

- # CR = number of subjects with a best complete response (confirmed + unconfirmed)
- # PR = number of subjects with a best partial response (confirmed + unconfirmed)
- N = number of subjects in the analysis set.

#### **14.2.3. ORR (for confirmed+unconfirmed responses) assessed by central radiologist review**

The BOR assessed by central imaging review will be derived as done for BOR assessed by local review (see section 14.2.2). See section 14.2.1 for handling of central review data.

Objective Response Rate, considered for confirmed + unconfirmed responses assessed by central radiologist review, will be analyzed in the same manner as the primary analysis for the ES and FAS.

#### **14.2.4. PFS based on investigator assessment**

PFS based on local review will be calculated and summarized using the KM method. The corresponding median PFS with 95% CI, 25th and 75th percentiles (Brookmeyer and Crowley 1982, Klein and Moeschberger 1997), as well as PFS estimated probabilities at selected time points (every 2 months up to 14 months) will be provided with 95% CI (Kalbfleisch and Prentice 2002) for the FAS and ES.

Progressive disease and death from any cause will be considered as events. If death or PD is not observed, the PFS will be censored at the date of last adequate tumor assessment prior to the cutoff date or new anti-tumoral treatment intake. However, if a PFS event is observed after more than 1 missing or inadequate tumor assessment, it will be censored at the last adequate tumor assessment. If a PFS event is observed after a single missing or non-adequate tumor assessment, the actual date of event will be used.

Censoring rules to be applied to the PFS endpoint are described in detail in

Table 12. Censor status will be summarized.

**Table 12: Censoring rules for PFS**

In the below table, “new antineoplastic therapy” refers to any additional secondary antineoplastic medication or anti-cancer surgery or radiotherapy.

	Situation	Event Date	Outcome
No baseline tumor assessments			
A1	No baseline assessment and death after the second scheduled post-baseline tumor assessment, or no death	Date of first study treatment administration	Censored
A2	No baseline assessment and death on or before the second scheduled post-baseline tumor assessment	Date of death	Event
No post-baseline tumor assessments (without new antineoplastic therapy given)			
B1	Death on or before the second scheduled post-baseline tumor assessment	Date of death	Event
B2	Death after the second scheduled post-baseline tumor assessment or no death	Date of first study treatment administration	Censored
With baseline and post-baseline tumor assessments (without new antineoplastic therapy given prior progression or death without progression observed)			
C1	Progression with zero or one missed/inadequate tumor assessment prior to progression	Date of progression	Event
C2	Death but no progression, with zero or one missed/inadequate tumor assessment prior to death	Date of death	Event
D1	Progression but two or more consecutively missed/inadequate tumor assessments prior to progression	Date of last adequate tumor assessment*	Censored
D2	Death without progression, but two or more consecutively missed/inadequate tumor assessments prior to death	Date of last adequate tumor assessment*	Censored
E	No progression, no death	Date of last adequate tumor assessment*	Censored
F	Treatment discontinuation due to ‘Disease progression’ without documented progression, i.e. clinical progression based on investigator claim	N/A (not considered as an event, patient without documented PD should be followed for progression after discontinuation of treatment)	Information ignored
Initiation of new antineoplastic therapy given prior progression or death without progression observed			
G	New antineoplastic therapy started before progression or death	Date of last adequate tumor assessment prior to initiation of new antineoplastic therapy*	Censored
H	No post-baseline tumor assessment and new antineoplastic therapy started prior to a death	Date of first study treatment administration	Censored

\* tumor assessment with non-missing and non-unknown overall lesion response, as defined in section 9.3.

The terms ‘adequate Tumor Assessments (TA)’ and ‘missing adequate TA’ are defined in section 9.3, together with rules to determine whether there is one or two missing/inadequate TAs (Table 8).

As sensitivity analyses, the analyses for PFS will be repeated with a censoring rule that includes a PFS event even if the event is recorded after 2 or more missing tumor assessments

**Table 13: Censoring rules for PFS (sensitivity analysis)**

*In the below table, “new antineoplastic therapy” refers to any additional secondary antineoplastic medication or anti-cancer surgery or radiotherapy.*

	Situation	Event Date	Outcome
No baseline tumor assessments			
A1	No baseline assessment and no death	Date of first study treatment administration	Censored
A2	No baseline assessment and death	Date of death	Event
No post-baseline tumor assessments (without new antineoplastic therapy given)			
B1	Death	Date of death	Event
B2	No death	Date of first study treatment administration	Censored
With baseline and post-baseline tumor assessments (without new antineoplastic therapy given prior progression or death without progression observed)			
C1	Progression	Date of progression	Event
C2	Death but no progression	Date of death	Event
E	No progression, no death	Date of last adequate tumor assessment*	Censored
F	Treatment discontinuation due to ‘Disease progression’ without documented progression, i.e. clinical progression based on investigator claim	N/A (not considered as an event, patient without documented PD should be followed for progression after discontinuation of treatment)	Information ignored
Initiation of new antineoplastic therapy given prior progression or death without progression observed			
G	New antineoplastic therapy started before progression or death	Date of last adequate tumor assessment prior to initiation of new antineoplastic therapy*	Censored
H	No post-baseline tumor assessment and new antineoplastic therapy started prior to a death	Date of first study treatment administration	Censored

\* tumor assessment with non-missing and non-unknown overall lesion response, as defined in section 9.3.

In addition to the primary analysis (i.e. Stage 2 or at Stage 1 if study stops for futility), the analyses for PFS will also be conducted at the time of the end of study.

PFS based on investigator assessment in the subgroup of subjects in Japan will be examined separately at the time of the primary analysis (i.e. Stage 2 or at Stage 1 if study stops for futility).

#### **14.2.5. PFS assessed by central radiologist review**

Analysis of PFS assessed by central radiologist review will be analyzed in a similar way of PFS based on local review for the FAS and ES.

PFS assessed by central radiologist review in the subgroup of subjects in Japan will be examined separately at the time of the primary analysis (i.e. Stage 2 or at Stage 1 if study stops for futility).

#### **14.2.6. Overall survival (OS)**

OS will be described using survival curves according to the Kaplan Meier method and reporting estimated median (in months) with 95% CI, 25th and 75th percentiles (Brookmeyer and Crowley 1982, Klein and Moeschberger 1997) and KM estimated probabilities with corresponding 95% CIs (Kalbfleisch and Prentice 2002) at several time points (every 2 months up to 14 months).

In addition to the Stage 1 and Stage 2 analyses, the analyses for OS will also be conducted at the time of the end of study.

OS in the subgroup of subjects in Japan will be examined separately at the time of the primary analysis (i.e. Stage 2 or at Stage 1 if study stops for futility).

#### **14.2.7. DOR based on investigator-assessed tumor evaluation**

Duration of response according to investigator will be calculated among the confirmed responders (i.e. CR and PR) from the time that measurement criteria are first met for complete or partial response (whichever status is recorded first) after first study treatment administration until the earliest date of progression or death due to underlying disease.

- Patients who are lost to follow-up, or reach the time point of analysis without a known record of progression or death will have the duration of response censored at the date of last adequate tumor assessment.

- Patients who received a new anti-tumoral treatment (chemotherapy, hormonotherapy, radiotherapy, surgery or other anti-tumoral treatment), whatever the type of treatment before their disease progression will be censored at their last adequate radiological assessment (i.e., at the date of last tumor assessment of CR, PR or SD).
- If an event is observed after a single missing or non-adequate tumor assessment, the actual date of progression will be used.
- If an event is observed after two or more missing or non-adequate tumor assessment, the duration of response will be censored at the date of last adequate tumor assessment.

**Table 14: Censoring rules for DOR**

In the below table, “new antineoplastic therapy” refers to any additional secondary antineoplastic medication or anti-cancer surgery or radiotherapy.

	Situation	Event Date	Outcome
With baseline and post-baseline tumor assessments (without new antineoplastic therapy given prior progression or death without progression observed)			
A1	Progression with zero or one missed tumor assessment prior to progression	Date of progression	Event
A2	Death (due to underlying disease) but no progression, with zero or one missed tumor assessment prior to death	Date of death	Event
B	Death (not due to underlying disease) but no progression, with zero or one missed tumor assessment prior to death	Date of last adequate tumor assessment*	Censored
C1	Progression but two or more consecutively missed tumor assessments prior to progression	Date of last adequate tumor assessment*	Censored
C2	Death without progression, but two or more consecutively missed tumor assessments prior to death	Date of last adequate tumor assessment*	Censored
D	No progression, no death	Date of last adequate tumor assessment*	Censored
E	Treatment discontinuation due to ‘Disease progression’ without documented progression, i.e. clinical progression based on investigator claim	N/A (not considered as an event, patient without documented PD should be followed for progression after discontinuation of treatment)	Information ignored
Initiation of new antineoplastic therapy given prior progression or death without progression observed			
F	New antineoplastic therapy started before progression or death	Date of last adequate tumor assessment prior to initiation of new antineoplastic therapy*	Censored

\* tumor assessment with non-missing and non-unknown overall lesion response, as defined in section 9.3.

Analysis of DOR will be described using survival curves according to the Kaplan Meier method and reporting estimated median (in months) with 95% CI, 25th and 75th percentiles (Brookmeyer and Crowley 1982, Klein and Moeschberger 1997) and KM estimated probabilities with corresponding 95% CIs (Kalbfleisch and Prentice 2002) at several time points (every 2 months up to 14 months).

DOR in the subgroup of subjects in Japan will be examined separately at the time of the primary analysis (i.e. Stage 2 or at Stage 1 if study stops for futility).

#### **14.2.8. DOR assessed by central radiologist review**

Analysis of DOR based on central review will be analyzed in a similar way of DOR based on local review.

DOR in the subgroup of subjects in Japan will be examined separately at the time of the primary analysis (i.e. Stage 2 or at Stage 1 if study stops for futility).

#### **14.2.9. TTR based on investigator-assessed tumor evaluation**

Time to first response will be calculated from the date of first study treatment administration up to the date of first documented CR or PR. The CR and PR does not need to be confirmed. Patients who do not achieve a PR or CR will be censored as follows (described in

Table 15):

- if they do not have a PFS event, they will be censored at the last adequate tumor assessment date. In this case patients have not yet progressed, so they theoretically still have a chance of responding;
- if they have a PFS event (i.e. progressed or died due to any cause), they will be censored at maximum follow-up (i.e., FPFV to LPLV used for the analysis, as defined in section 9.1.2). In this case, the PFS event is the worst possible outcome as it means the patient cannot subsequently respond. Since the statistical analysis makes use of the ranking of times to response it is sufficient to assign the worst possible censoring time which could be observed in the study which is equal to the maximum follow-up time (i.e., time from FPFV to LPLV).

**Table 15: Censoring rules for TTR**

In the below table, “new antineoplastic therapy” refers to any additional secondary antineoplastic medication or anti-cancer surgery or radiotherapy.

	Situation	Event Date	Outcome
A	Documented Response (CR or PR)	Date of first documented response	Event
B	Progression or death	Censoring time assigned to maximum follow-up time: - Time to Event Origin Date = date of first study treatment administration - event date = date of first study treatment administration + (LPLV – FPFV)	Censored
C1	No adequate post-baseline tumor assessment* and no death	Date of first study treatment administration	Censored
C2	No progression, no death	Date of last adequate tumor assessment*	Censored
D1	No adequate post-baseline tumor assessment* and new antineoplastic therapy started before death	Date of first study treatment administration	Censored
D2	New antineoplastic therapy started before progression or death	Date of last adequate tumor assessment prior to initiation of new antineoplastic therapy*	Censored

\* tumor assessment with non-missing and non-unknown overall lesion response, as defined in section 9.3.

TTR will be described using survival curves according to the Kaplan Meier method and reporting estimated median (in months) with 95% CI, 25th and 75th percentiles and KM estimated probabilities with corresponding 95% CIs at several time points (every 2 months up to 14 months).

TTR will be also analysed for confirmed responders only.

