8. ASSESSMENTS

8.1. EFFICACY ASSESSMENTS

Tumor response will be evaluated locally by the Investigator according to RECIST, v1.1 (**Section 17.6**).

All potential sites of tumor lesions will be assessed at screening, the following should be performed:

- A CT scan with IV contrast of chest, abdomen and pelvis is the preferred technique. If there is concern about radiation exposure, an MRI may be used instead of a CT.
- In subjects with a history of asymptomatic brain metastases, a brain MRI or CT scan
- If clinically indicated, a whole-body bone scan (i.e., if bone metastases are suspected or known at baseline). A whole-body bone imaging method may be used per local standard of care (e.g., Tc99m bone scan, fluorodeoxyglucose-positron emission tomography [FDG-PET], sodium fluoride-positron emission tomography [NaF PET] scan or whole-body bone MRI).

Skeletal lesions identified on a whole-body bone scan at baseline, which are not visible on the chest, abdomen, or pelvis CT (or MRI) scan should be imaged at baseline using localized CT, MRI, or X-ray.

As far as possible, the same method of assessment of each lesion should be used at screening and for all visits, for consistent comparison.

During the Main study period, all post-screening assessments should be performed every 6 weeks (± 7 days) from the first dose for the first 12 weeks of treatment; except for first tumor evaluation for which the time-window allowed is day 42 ± 7 days from first dose. Then, every 8 weeks thereafter until disease progression, subject decision, withdrawal of consent, initiation of subsequent anticancer therapy, subject is lost to follow-up, death or defined end of study as described in **Section 5.7**.

During the Study extension period, all assessments should be performed every 12 weeks (± 7 days), until disease progression, subject decision, withdrawal of consent, initiation of subsequent

anticancer therapy, subject is lost to follow-up, death or defined end of study as described in **Section 5.7**.

If a subject discontinues study treatment for reasons other than disease progression, tumor assessments must continue to be performed (as per local and central review) every 6 weeks (first 12 weeks) then every 8 weeks during the Main study period and every 12 weeks during the Study extension period (as per local review), until the start of new anti-cancer therapy, disease progression, death, lost to follow-up, subject decision or withdrawal consent.

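### TTR Table 15 rows D1/D2 censor non-responders who start new therapy as if they could still respond, which can overstate the Kaplan-Meier probability of response; precedence over row B is not stated

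*SAP*

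**What the plan says.** SAP 14.2.9 has two censoring rules for subjects without a CR or PR, each with a reason.

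- Without a PFS event: "if they do not have a PFS event, they will be censored at the last adequate tumor assessment date". The reason given is "In this case patients have not yet progressed, so they theoretically still have a chance of responding".
- With a PFS event, glossed there as progression or death from any cause: censored at maximum follow-up, because "the PFS event is the worst possible outcome as it means the patient cannot subsequently respond".

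Table 15 turns these into rows. Row B (progression or death) uses maximum follow-up. Rows C1/C2 use first dose or the last adequate scan. Two further rows cover new therapy, which includes surgery and radiotherapy:

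- D1, "No adequate post-baseline tumor assessment* and new antineoplastic therapy started before death": censored at first dose.
- D2, new therapy before progression or death: censored at "Date of last adequate tumor assessment prior to initiation of new antineoplastic therapy".

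Three other places matter.

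- SAP 14.2.2, with the same rule in 14.1, on what counts toward best response: "Only tumor assessments performed before the start of any further antineoplastic therapies".
- Protocol 8.1, on subjects who stop treatment without progression: scans continue "until the start of new anti-cancer therapy, disease progression, death, lost to follow-up, subject decision or withdrawal consent".
- SAP Table 12: row F ignores treatment discontinuation "without documented progression, i.e. clinical progression based on investigator claim", and rows G/H censor PFS when new therapy comes first.

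TTR is reported as Kaplan-Meier probabilities every 2 months to 14 months, by local and by central review. A further analysis is limited to confirmed responders.

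**The concern.** Maximum-follow-up censoring keeps patients who cannot respond in the risk set, so that the curve levels off at the proportion who did respond. A non-responder who starts new therapy is in the same position: later scans do not count toward best response, and protocol scanning stops. Rows D1/D2 nevertheless remove that patient early, which is the treatment 14.2.9 justifies by a remaining chance of response. Each later response is then divided by a smaller risk set.

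The situation is foreseeable. Take stable disease at week 6, clinical deterioration without a scan, second-line therapy at week 9 and death at month 6. Table 12 rows F and G leave this patient with a censored PFS time. For TTR, row D2 gives week 6, while row B, which covers death, gives maximum follow-up. Table 15 states no order, so two programmers could differ.

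At stake is a named secondary endpoint whose curve will be read beside the ORR from the same patients and could exceed it.

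**Working it through.** The documents state no TTR figure, so there is none to reproduce. They also give no number of D1/D2 patients, so the counts and response times below are assumptions.

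**Inputs.** N = 90 (SAP 6.5) and scans at weeks 6, 12 and 20 (protocol 8.1). Assumed: 45 responders, 31/9/5 at those scans; x affected non-responders; all other non-responders held to maximum follow-up under row B. Patients censored on a scan day count as at risk on that day. The quantity is 1 − KM at 14 months.

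**With row B's censoring time for the x patients:** 45/90 = 50.0%, whatever x is.

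**Under Table 15 as written:**

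- D1, censored on day 1: 45/(90 − x).
- D2, censored at week 6: the survival factors are 59/90, then (50 − x)/(59 − x), then (45 − x)/(50 − x). So 1 − KM = 1 − (59/90) × (45 − x)/(59 − x).
- D2, censored at week 12: 1 − (50/90) × (45 − x)/(50 − x).

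For x = 9 these are 45/81 = 55.6%; 1 − 0.6556 × 36/50 = 52.8%; and 1 − 0.5556 × 36/41 = 51.2%.

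| Affected patients x | D1, day 1 | D2, week 6 | D2, week 12 | After last response |
|---|---|---|---|---|
| 3 | 51.7% | 50.8% | 50.4% | 50.0% |
| 6 | 53.6% | 51.8% | 50.8% | 50.0% |
| 9 | 55.6% | 52.8% | 51.2% | 50.0% |
| 12 | 57.7% | 54.0% | 51.8% | 50.0% |

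**Second example, nearer the design rate of 45%.** Assume 41 responders of 90 (45.6%), either 25/10/4/2 or 16/12/8/5 at weeks 6/12/20/28. Nine affected patients give:

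- D1: 41/81 = 50.6%.
- D2 at week 6: 48.4% to 49.4%.
- D2 at week 12: 46.9% to 48.0%.
- D2 at week 20: 46.0% to 46.7%.

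Eight D1 patients are enough to make a median TTR estimable (41/82 = 50.0%) although only 45.6% responded.

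The shift cannot be negative: early censoring lowers later numbers at risk without lowering the number of responses.

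**The case against.** A reader might infer that rows D1/D2 break the SAP's own rule. They do not. Table 12 rows G/H leave these patients without a PFS event, and SAP 14.2.9 and 6.3.2 censor non-responders without a PFS event at the last adequate assessment. Protocol 13.2.2 censors every non-responder there. The conflict is with the reason stated in 14.2.9, not with the wording of the rule.

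Censoring at new therapy is also a recognised choice, used here for PFS and DOR, and a patient with stable disease who goes to resection is hardly a worst outcome. That is fair as a matter of clinical standing. The SAP's argument, however, turns on whether a response can still occur, and for that patient no counted response can.

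The proposed change is not a complete cure. Sections 14.1 and 14.2.2 also exclude scans more than 30 days after the last dose, so some C1/C2 patients equally cannot respond yet keep early censoring. After the fix the plateau equals the crude rate only if no C1/C2 patient is censored before the last response.

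Finally, consequence is limited. SAP section 8 makes everything except the primary test exploratory, and response rates are reported directly with full denominators. This lowers the weight of the point but does not remove it.

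**Conclusion.** The point holds as a conflict between Table 15 and the rationale in SAP 14.2.9, together with an unstated row order. The curve can be overstated; it would go too far to say that it is. The effect requires at least one D1/D2 patient censored before the last observed response and is zero otherwise. In the first example, 3 to 12 such patients add 1.7 to 7.7 points if all are D1, 0.8 to 4.0 if last scanned at week 6, and 0.4 to 1.8 if last scanned at week 12. These sizes rest on assumed counts and response times.

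A reader might also infer that the trial's response rate is inflated. The documents do not support that: cORR and ORR divide by all subjects in the analysis set, and the confirmed-responder TTR contains no D1/D2 patients. Only the all-subjects TTR analyses, local and central, are touched.

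**What to change.** In Table 15, give non-responders in rows D1 and D2 the maximum-follow-up censoring time of row B, and keep last-scan or first-dose censoring for C1/C2.

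State row precedence: a documented response before new therapy first (A), then B, D1 and D2, then C1/C2 for those remaining. Once B and D share a censoring time, their order no longer changes the result. The order of D over C does: a living patient who has started new therapy without progression also fits the wording of C1 or C2.

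Align the text of SAP 14.2.9 and 6.3.2, and list the departure from protocol 13.2.2 in SAP section 20. Row B already departs from that protocol rule and section 20 does not mention it, so one entry can cover both.

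The cost is two table cells, a precedence note, short text edits and a small programming change. The Kaplan-Meier response probabilities become slightly less favourable.
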